All subjects who participate in PGT-SC genetic testing will receive a telephone call two weeks after results are mailed, to assess PGT-SC result comprehension and potential distress (see Two Week Risk Feedback Comprehension Assessment) and to answer any questions they may have. All those who

complete this Assessment will receive a \$5 Target Gift card as thanks for their effort. Based on prior literature documenting low levels of distress in those undergoing genetic testing for high-risk mutations, and among those found to carry *CDKN2A* mutations, we anticipate low levels of distress regarding PGT-SC feedback. Anyone who reports high distress will be referred to Clinic Director and Co-Investigator [name], who addresses distress issues regularly in the UNM clinic. If they wish, a genetic counselor will be available.

E) Three-month follow-up.

All participants who completed Baseline Assessments (whether tested or not) will be contacted for assessment by telephone three months after PGT-SC testing (Three Month Follow Up Questionnaire). Participants who complete this three-month follow up assessment will receive a \$15 Target Gift card for their valued study participation.

F) Group 1 genetic testing option.

Those 120 participants randomized to the control group will receive an offer for PGT-SC directly after the three-month follow-up assessments. They will be offered testing, and of those who pursue testing, will receive results by mail or by email, sent by the PA who enrolled them, and a two-week follow-up telephone call to assess result comprehension and potential distress.

G) Summary.

We anticipate that patients will be enrolled over an approximately 12 month period, complete assessments and receive feedback within 20 months. Thus individuals are estimated to be in the study for 3 months and the enrollment and assessment period overall will last as long as 20 months total. Primary analyses will be completed in the 6 months following the 24 months period of participation; the entire study will take 3 years.

9) Study Endpoints.

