Primary endpoints are based on the 3-month follow up questionnaires. The primary study endpoints include personal utility of Personal Genomic Testing for Skin Cancer (PGT-SC) in terms of short-term (three months after testing) sun protection, skin screening (i.e., behaviors), communication, melanoma threat and control beliefs (i.e., putative mediators of behavior change), as well as differential reach of PGT-SC across Hispanics and non-Hispanics, as well as potential explanations for any differential reach. These will include the construct/measures listed below:

Construct/Measure	Prior work/psychometrics	Assess point
Sun protection and skin screening (Sunscreen, shade seeking, clothing and hat usage) on separate 5-point scales (never-always); health provider screening (no/yes).	Item reliability $\geq 80\%$. (Ganz, 2008)	B, 3-month
Family/physician communication. Frequency, content of communication with physicians, family, and friends regarding skin cancer risk, interest in genetic information; 4-point scales (not at all-a lot).	Items used with high comprehensibility in population-based studies ([name] 2005, 2009, 2012, 2014)	B, 3-month, (interest in genetic information only)

Perceived skin cancer threat belief (Witte 1996). Includes assessment of risk perceptions (verbal, percent likelihood, comparison) on separate scales (5 to 10-point) from low-high, with “don’t know” option (Waters 2013); worry, assessed with 4-point items (never-all the time). Perceived skin cancer control beliefs (Witte 1996) Includes skin cancer prevention self-efficacy (7 items, on separate 4-point scales; not at all-extremely capable), skin cancer prevention response-efficacy (7 items, on separate 4-point scales; not at all to extremely important).
	
Widely used perceived risk items drawn from prior health behavior research (Weinstein 1982), Lerman’s cancer worry scale (Lerman 1991), and perceived cancer severity (Aiken 1994). Control belief items (Bandura 1986) predicting uptake of cancer prevention behaviors; adapted for skin cancer prevention ([name] 2006).
	
B, 3-month (risk perception question only)

Hispanic ethnicity
	
For initial sampling frame (50%) Hispanic, self-report as per Baseline survey.
	
B

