Cognitive interviews to ensure high comprehensibility and acceptability of the translations will be conducted by [name] and [name].

The Department of Psychiatry & Behavioral Sciences at MSKCC will conduct data analysis on de-identified data.

11) Study Methods

*The timeline above gives very detailed information about study methods.

Subjects will be approached at their Clinic and asked if they are interested in participating. Individuals accompanying Clinic patients and who attend another UNM Clinic are eligible to participate.

They will then discuss the study with the bilingual interviewer and, if they are eligible agree and sign informed consent. All baseline surveys will then be completed with the PA in the clinic.

Identifiers will be collected and remain at UNM for mailing and follow-up. Subjects will then be de-identified at the end of the study (after 3 years).

Subjects will receive compensation for participation. ALL consented subjects will receive a \$15 Target Gift card after completion of the Baseline Questionnaire; those in the randomized to the wait list control Group 1 will receive compensation for the baseline survey and the three-month survey. Those randomized to Group 2, the PGT-SC arm will then be given information modules through the internet (or on paper if they prefer). They will be asked if they would like to participate in genetic testing for MC1R. Those randomized to receive PGT-SC who complete the online educational modules will be compensated \$5 Target Gift card per educational module, with a maximum of \$15 possible.

Additionally, among those who elect genetic testing, we will assess distress levels two weeks after the PGT -SC genetic results have been received, and will compensate participants for their time with a \$5 target Gift card. All participants who completed Baseline Assessments (whether tested or not) will be contacted for the final assessment by telephone approximately three months after recruitment.

Participants who complete the three-month outcome assessment will receive a \$15 Target Gift card. This level of compensation is reasonable for the level of effort required for subjects.

12) Data and Specimen Banking

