For participants who indicate that they want to participate in genetic testing, we will mail saliva collection kits. They will give a sample of saliva and mail these back to the study in pre-addressed, stamped envelopes. These will be delivered to the UNM Molecular Epidemiology Laboratory at UNM HSC. DNA will be extracted and sequenced for MC1R only, a gene that is important for pigmentation. Specimens will be destroyed when a good test result is obtained. Data will be kept until the end of the study when it will be destroyed. [name], the Manager of the Molecular Epidemiology Laboratory, will be the only person with access to the specimens. Each specimen will have a separate ID number that links it to the donor. When the specimen has been assayed, the de-identified information will then be given to the study team ([name], [name], data analyst) and to the donor.

No information, other than participant study number, will be stored with the specimen. Results will be identifiable to authorized personal at UNM (PAs, [name] and [name]) until the end of the study. Genetic testing will be done for MC1R only by sending the DNA from the participants to an outside accredited laboratory but will be completely de-identified.

SOMBRA Protocol for DNA Extraction

Important Points before starting:

- Perform all centrifugation steps at room temp (15-25°C)
- Preheat the water bath at 56°C.
- If Buffer AL or Buffer ATL contains precipitates, dissolve by heating to 70°C with gentle agitation.
- Make sure Buffer AW1 and Buffer AW2 are prepared (follow specified instructions) before purification steps are initiated.

Day 1:

1. Add 500 μ l of 100% ethanol to each sample and mix by inversion (or vortexing) for one minute. The tissue will now appear chalky white.
2. Centrifuge the samples at 12,000 rpm for 5 minutes at room temperature and remove the supernatant.
3. Repeat step 1 and 2 once for a total of two ethanol washes.
4. Dry the tissue pellet by inversion under the hood until the ethanol is evaporated. This may take anywhere from 25-60 minutes depending on pellet size. At this point the pellet can be frozen at -80C or proceed with the next step.
5. To the pellet, add 120 μ l of Buffer ATL, and 20 μ l Proteinase K (QIAGEN; 20 μ g/ μ l stock). Mix thoroughly by pulse-vortexing for 15 sec. (note: begin this step in the morning)

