This is a minimal risk study; there are no physical risks posed by this study. However, it is possible that receiving information about one's risk for skin cancer could cause psychological distress. We will monitor subjects closely who receive that information. In the Randomized Clinical Trial, there is potential risk of loss of privacy given that the Baseline Assessment might be conducted in the clinic waiting room.

We will give the genetic results by mail (or email, if requested); the PA who enrolled the participant will mail or email that information. If the participant has concerns, then an appointment with a [name] will be made, so that he/she can discuss these further.

As research has the possibility of breach of confidentiality, all possible efforts are made to limit that risk.

17) Potential Benefits to Subjects

Potential benefits include learning more about skin cancer prevention and skin cancer risk awareness. Although we cannot guarantee that participants may benefit directly from study participation, prior study participants have reported that they enjoyed providing researchers with greater knowledge of their experience in hopes of facilitating the design of cancer prevention materials and in possibly benefiting others. Given the potential gains to participants, the ratio of risk to benefits is quite low and reasonable.

18) Vulnerable Populations

N/A

19) Multi-Site Research

[name] of the University of New Mexico and [name] at Memorial Sloan-Kettering are Multiple-Principal Investigators. [name] is supervising the data collection in New Mexico and [name] is supervising the data analyses in New York. We plan to use the UNM HRRC as the central IRB of record. Both sites have had input into the development of the protocol, consent documents and HIPAA Authorization. All required approvals will have been obtained at both UNM HRRC and MSKCC. Any modifications will be communicated to each site, including approval by the site's IRB of record. As noted elsewhere in the protocol, all engaged participating sites will safeguard data as required by local information security policies. Any non-compliance with the study protocol or applicable requirements will be reported in accordance with local policy.

The proposed research is a low-risk behavioral trial. Research staff will carefully monitor each participant's emotional reaction during study interviews, and offer referral when appropriate.

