Phase II: Our bilingual PAs will approach primary care patients in the UNM 1209 Clinic, the Orthopedic Clinic at OSIS, the Family Medicine Clinic, the Center for Employee and Occupational Health Services or the North Valley Clinic with NCI Skin Cancer Pamphlets (available in English and Spanish versions; “Anyone can get skin cancer,” <https://pubs.cancer.gov/ncipl/detail.aspx?prodid=P237>). They will explain the study and review the informed consent and HIPAA documents in English or in Spanish. If the potential participant decides to enroll, they will then be given a Screening Survey, sign the Consent form and HIPAA (and receive a copy for themselves) and a Baseline Questionnaire in a private area of the Clinic.

The potential participant will have as much time as he or she wishes to decide to participate. At each subsequent contact, once an individual has been consented, the PA will make sure that the participant wishes to continue by asking such questions as “Do you have any new questions or concerns?”

28) **Drugs or Devices**

N/A

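### The plan neither names nor masks the person who makes the 3-month call, and the staff most likely to make it would usually know the arm and could know the result

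*Combined protocol and SAP*

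**What the plan says.** Section 9 states "Primary endpoints are based on the 3-month follow up questionnaires". Sun protection is self-rated on 5-point frequency scales, provider screening is a yes/no self-report, and the communication and belief items are rating scales.

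Two places describe the 3-month contact. Section 8 E says participants "will be contacted for assessment by telephone three months after PGT-SC testing"; section 11 says they "will be contacted for the final assessment by telephone approximately three months after recruitment". Both are in the passive and name no caller. They also start the clock at different points. Section 8 F adds that the 120 controls "will receive an offer for PGT-SC directly after the three-month follow-up assessments".

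On the PAs:
- Section 22 gives them the interviewing role.
- Section 8 C has them facilitate the baseline questionnaire, with randomisation following it. Section 22 has participants leave with an introduction letter that differs by group.
- Section 16, on genetic results: "the PA who enrolled the participant will mail or email that information".
- Section 12: "Results will be identifiable to authorized personal at UNM (PAs" and certain others, until the study ends.
- Section 27, Phase II: "At each subsequent contact, once an individual has been consented, the PA will make sure that the participant wishes to continue".

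No section masks anyone to arm or result, assigns a separate outcome interviewer, or says that assessment is open.

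**The concern.** Frequency ratings given aloud to an interviewer can be moved by how a question is put, how a hesitant answer is coded, and what the respondent thinks the listener wants to hear. If the caller knows that the person was tested, declined or was a control, the first two can differ between groups. If the caller also sent that person's genetic result, the third can differ as well. The Aim I hypothesis is directional (testers higher than decliners or wait-list controls), so staff who know it have an expectation to carry into the call.

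Participants cannot be masked, but the caller can be, at least in part. What is at stake is the credibility of the behaviour, communication and belief comparisons at 3 months. An arm difference could not be cleanly separated from a difference in how answers were obtained.

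**Working it through.** **Step 1: what can be established about the caller.** The plan has no figure to reproduce here, so the check is a reading of the sections against each other.

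| Question | What the plan supports |
|---|---|
| Who calls at 3 months? | Not stated (8 E, 11). The PAs are the natural reading: they are the interviewers (22), and a PA is placed at each later contact (27). |
| Would a PA know the arm? | Usually. Randomisation follows the PA-run baseline (8 C), and the take-away letters differ by group (22). |
| Would a PA know the result? | Only PGT-SC participants who were tested have one by then. The enrolling PA sends it (16), and PAs as a group can identify it (12). |
| Does scheduling reveal status? | Yes, if the call is timed from testing (8 E), because the scheduler must know who tested and when. Decliners and controls have no such date. Timing from recruitment (11) reveals nothing. |
| Which endpoints are exposed? | Those on the 3-month questionnaire. The main reach measure is the decision registered after module 4 (8 D), so no 3-month interviewer takes it. |

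**Step 2: how much a differential bias could matter.** This is an illustration. The documents give neither a bias size nor an alpha, so two-sided 0.05 and the bias values (in SD units) are assumptions.

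Inputs: 120 control and 530 PGT-SC (section 8 C); up to 20% unreachable at 3 months (section 13). Analysed: 120 × 0.8 = 96 and 530 × 0.8 = 424.

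SE of a standardised mean difference = √(1/96 + 1/424) = 0.113.

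Difference detectable with 80% power = (1.960 + 0.842) × 0.113 = 0.317 SD.

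False-positive rate with no true effect and bias b = Φ(b/SE − 1.96) + Φ(−b/SE − 1.96). For b = 0.10, b/SE = 0.885, giving Φ(−1.075) + Φ(−2.845) = 0.141 + 0.002 = 14.3%.

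| Differential bias (SD) | 96 vs 424 | 120 vs 530 (no loss) |
|---|---|---|
| 0 | 5.0% | 5.0% |
| 0.05 | 7.3% | 7.8% |
| 0.10 | 14.3% | 16.7% |
| 0.15 | 26.4% | 31.7% |
| 0.20 | 42.5% | 50.7% |

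**Step 3: if only testers' answers shift.** Arm-level shift = tester share × shift per tester. For the share, take 15% to 50%. The lower value is 0.30 registering a decision × 0.50 returning a sample (8 D); as the 0.50 is itself given as a maximum, the share could be lower. The upper value is the top of the 30–50% acceptance range in section 6. With an assumed shift of 0.1 to 0.2 SD per tester, the arm-level shift runs from 0.15 × 0.1 = 0.015 SD to 0.50 × 0.2 = 0.10 SD. The false-positive rate at those ends is 5.2% (b/SE = 0.133; 0.034 + 0.018) and 14.3%. The contrast of testers with the other groups carries the full 0.1 to 0.2 SD.

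**The case against.** The strongest reply is that the plan is silent, not wrong. A reader might infer that the endpoints are in fact collected by people who know arm and result. The documents do not support that as a statement of fact:

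- The caller is never named, and nothing says what the caller has in view. Access to results under section 12 does not mean having them open during the call.
- The wording on the control offer gives a sequence. It does not show one call or one person, and the arm could be revealed at the end.
- Section 8 F also says that controls who test "will receive results by mail or by email, sent by the PA who enrolled them". Those results go out after the primary assessment and cannot influence it.
- The section 27 sentence concerns continued willingness. It refers to the PA, and not specifically to the one who enrolled the participant.

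A reader might also infer that the bias acts only in the PGT-SC arm and favours the intervention. That does not follow. A caller who knows someone is a control can code differently too, and participants in both arms met a PA at baseline. Nor can it be said that the bias would hide a fall in sun protection after average-risk feedback (Aim Ia). A caller aware of that worry might lean the other way, and a uniform shift within that subgroup moves the average level but not the coefficients of the baseline predictors that Aim Ia studies.

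Two further points stand. Fixed-response items leave less room for coding differences than open questions would. The tester contrast is self-selected, so masking the caller cannot make it a randomised comparison.

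What survives is that subjective endpoints are left, by default, to staff who would usually know or could look up the allocation, with no safeguard and no acknowledgement.

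**Conclusion.** The point holds as a gap in trial conduct: the 3-month caller is unnamed and unmasked, and the PAs are the likely callers. It applies to the self-reported behaviour, communication and belief items taken at 3 months, and not to the registered test decision that is the main measure of reach.

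The bias has no known size or direction. The range of 7.3% to 42.5% rests entirely on assumed biases of 0.05 to 0.20 SD and an assumed alpha of 0.05. If only testers shift, the arm-level bias is 0.10 SD or less under the stated assumptions, which is below one standard error. It is a matter the plan should deal with because the remedy is cheap, and not because serious bias has been shown.

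**What to change.** In section 8 E and 8 F:

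1. Have each 3-month call made by an existing PA who did not enrol that participant, send their result or make their two-week call.
2. Give the caller a list with ID, name, telephone number and language only.
3. Time the call from recruitment or randomisation in both arms, and reconcile sections 8 E and 11 accordingly.
4. Ask participants at the start not to mention group or result. Ask the behaviour and belief items before any test-related or distress items, if the questionnaire does not already do so.
5. Release the arm, and make the Group 1 offer, only after the questionnaire is locked.
6. Record whether the caller became unmasked, and when.

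Distress monitoring and referral continue as planned.

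Cost: some scheduling work, a revised call list and script, and loss of continuity with the enrolling PA for one call. Timing from recruitment or randomisation also means that testers are interviewed less than three months after their result, so the definition in Aim I and section 9 would need to be aligned. The gain is partial, since participants know their own arm and some will reveal it.

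The plan refers to PAs in the plural but gives no number. If there are too few to reassign calls, section 8 E should state that assessment is open and the report should list this as a limitation.

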- 1) **Personalized Genomic Testing for Skin Cancer – Maximizing Utility and Reach – 05/16/17**
- (v. 10)
- 2) **IRB Review History N/A**
- 3) **Objectives**

This study will have two phases, with an added usability test after Phase I and before Phase 2. Phase 1: Cognitive Interviews in Spanish.

Phase 2: Personalized Genomic Testing for Skin Cancer (PGT-SC).

The overarching goal of this study is to learn more about how to maximize the availability, comprehension and appropriate uptake of personalized genomics among different populations in New Mexico. The proposed study has been funded as an R01 by NCI for three years.

Aim I: To examine the personal utility (that is, how does personal genomic testing help the individual) of Personal Genomic Testing for Skin Cancer (PGT-SC) in terms of short-term (three months after testing) sun protection, skin screening (i.e., behaviors), communication, melanoma threat and control beliefs (i.e., putative mediators of behavior change). Guided by Protection Motivation Theory (Robberson and Rogers, 1998), **we hypothesize that behaviors and putative mediators will be higher in those who test, compared to those who decline testing or wait-list controls.**

Aim Ia. An important challenge of personal genomics involves the potential for those who receive “negative” genetic feedback to increase risky behaviors (McBride et al., 2010). To examine this potential unintended consequence of testing, we will conduct a subgroup analysis among those who receive average risk PGT-SC findings, examining sun protection at three months as the outcome. Predictors will include baseline skin cancer threat and control beliefs, skin cancer risk factors, and demographics. These findings will be used in future studies to develop messages for groups that receive average risk feedback, which accounts for large segments of those tested for moderate risk susceptibility factors across many diseases.

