Personalized genomic testing for skin cancer (PGT-SC) is an ideal context to extend Multiplex to a new population, and new outcomes. Skin cancers are preventable, curable, very common in the general population (Lazovich et al., 2012), and disproportionately increasing in Hispanics (Rouhani et al., 2010). The NHGRI Multiplex Study offered testing for melanoma risk via the melanocortin 1 receptor gene (*MC1R*) (Wade et al., 2010) because *MC1R* is common in the general population (50% \geq 1 high risk variant) (Demenais et al., 2010), interacts with sun exposure (Udayakumar and Tsao, 2009), and confers risk (2-3 fold (Raimondi et al., 2008); consistent with most moderate risk variants), *even in those with darker skin types*. *MC1R* feedback is a promising vehicle to raise risk awareness and protective behavior in the general population, including Hispanics who are largely unaware of their melanoma risks (Friedman et al., 2994; Hu et al., 2009; Piptone et al., 2002; Robinson et al., 2011). We will conduct a randomized controlled trial examining internet presentation of the risks and benefits of PGT-SC (shown to be feasible in Multiplex) versus wait-list controls who are not offered testing, comparing personal utility and reach in a general population, English or Spanish-speaking cohort in Albuquerque, New Mexico, where there is year-round sun exposure.

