University of New Mexico (UNM) primary care patients are receptive to skin cancer genomic communication; UNM Hispanics report higher skin cancer misconceptions. Drs. [name] and [name] conducted a pilot study in the UNM 1209 Clinic to examine 1) patients' receptivity to behavioral research studies in skin cancer and genetics, 2) to document levels of sunscreen and protective clothing use, shade-seeking, and health provider skin cancer screening examinations, 3) to examine prior health information-seeking and family cancer discussions, and 4) prevalence of accurate skin cancer beliefs. Most (71%) participants were female and they ranged in age from 19-81 years (n=50), with racial/ethnic subgroups consistent with the Albuquerque population (46% were Hispanic, 35% were Non-Hispanic White, 6% Native American, 3% African American, and 10% other). Nine percent had not completed high school, and 55% had household incomes less than \$30k/year. About one third (30%) reported a family skin cancer history and 7% a personal skin cancer history. About two-thirds (66%) reported interest in behavioral skin cancer research, and while few (17%) had heard of genetic testing marketed directly to consumers, two thirds (76%) said they would be interested in learning more about genetic testing for skin cancer. Sun protection and skin cancer screening levels were consistent with recent national data; 29% reported that they consistently used sunscreen, 62% wore a shirt with sleeves, 34% a hat, and 47% sought shade often or always while outside on a sunny day. Even fewer (26%) had ever received a health provider skin examination. Non-Hispanic Whites reported more consistent use of sunscreen, and were more likely to have received a prior health provider skin examination than Hispanics and other racial/ethnic groups (all p values <0.01). Two-thirds (62%) reported that they were moderately or highly likely to develop skin cancer. Predominant reasons for heightened risk included current or past sun exposure, fair skin, and family history or genetic factors. Spontaneous health information-seeking was common, with 72% reporting that they had ever sought information on medical topics, predominantly via the internet. Over half (62%) had sought cancer information. About half (55%) had talked about cancer risk, and 37% about skin cancer risk, in their family. Those with higher perceived skin cancer risk talked more about it with their family ($r=0.34$, $p=0.001$) and were more interested in skin cancer behavioral research participation ($r=0.26$, $p=0.01$). We assess skin cancer misconceptions as an explanation for reduced PGT-SC reach in Aim II of the current study, because Hispanics reported more skin cancer misconceptions than Non-Hispanic Whites in our UNM pilot study. Over half of Hispanics endorsed confusion about which skin cancer recommendations to follow, and significant proportions of Hispanics agreed with the statement "it seems likely almost everything causes skin cancer" (24%); and "people with skin cancer would have pain or other symptoms prior to diagnosis" (24%; Torres et al., 2014). Also in our prior work with nationally representative samples, we found that Non-Hispanic Whites had higher awareness of accurate skin cancer causes, prevention strategies, and symptoms than Hispanics. Hispanics reported higher levels of information overload and misconceptions. ([name] et al., 2009).

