We will share results of genetic testing with individual study participants (SOMBRA Result A – average risk results, and SOMBRA Result B – increased risk results). The results are **not actionable, but informational**. The PA will mail results to the study participant as was done in the Multiplex Study, or if the participant wishes – by email. If there are any signs of distress in any way, we will work with [name], the Director of the Clinic, and with [name], a cancer genetic counselor at the UNM Cancer Center, as necessary. Additionally, we will be assessing distress levels two weeks after the PGT-SC results have been received, and at all follow-up time points. Through the ongoing monitoring process of the study (e.g., regular meetings with research staff), the PIs and Co-Investigators will be informed of any concerns/distress that occur among study participants.

22) **Resources Available**

Qualifications of Investigators: [name] has been conducting epidemiologic research internationally and locally for the past 27 years. Her CV is attached. [name] has been conducting psychological and behavioral research for more than 15 years. Her CV is attached.

Project Assistants will interview individuals who agree. They are bi-lingual in English and Spanish, with either a Bachelor's degree and at least two years' experience that is applicable to the duties listed in the job description, or a Master's degree with at least six

months' experience that can be demonstrated to be applicable to the duties listed in the job description.

Recruitment plan/access to potential recruits. [name], Director of the 1209 UNM Primary Care Clinic, is a co-investigator and will assist the study with logistics at the Clinic and in working with the Clinic staff. Previously, we conducted a pilot study of 100 patients at the clinic with positive results and no negative feedback.

We will post a flyer (Clinic Flyer) explaining the study to the population of individuals attending the Clinic. In the pilot study, we recruited 100 patients in 3 days; therefore, our plan to spend several months to recruit 885 patients seems quite feasible. We will meet with the staff at the clinic to explain our goals. There are quiet spots within the clinic where we can easily discuss the study with interested individuals, explain Informed Consent and HIPAA and conduct the Baseline Questionnaire.

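### Sun protection is analysed over about a year of interviews with no season term: a small precision loss in the randomised contrast, and a possible confounder in Aim Ia and the tester comparisons

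*Combined protocol and SAP*

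**What the plan says.** Section 9 (Study Endpoints) lists sun protection among the primary endpoints and measures it by "Sunscreen, shade seeking, clothing and hat usage) on separate 5-point scales (never-always", at baseline and three months. It states no recall window or reference season.

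On the calendar, Section 8 G says "We anticipate that patients will be enrolled over an approximately 12 month period". Section 22 (Resources Available) suggests something shorter: "our plan to spend several months to recruit 885 patients seems quite feasible". (The total in that sentence differs from the 650 to be randomised. That is a separate matter and is not used here.)

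Aim Ia in Section 3 is a subgroup analysis of people who receive an average-risk result, "examining sun protection at three months as the outcome". Its predictor list reads: "Predictors will include baseline skin cancer threat and control beliefs, skin cancer risk factors, and demographics". Neither season nor interview month appears, and no comparator is named. Aim I compares testers with decliners or wait-list controls. The data processing text in Section 13 covers distributions, intention to treat, missing data and multiplicity, but not calendar time.

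The follow-up call has two anchors. Under Section 8 E, participants "will be contacted for assessment by telephone three months after PGT-SC testing"; Section 11 puts the final call about three months from recruitment.

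**The concern.** How often people use sunscreen, shade, a hat and covering clothing may vary over the year. With enrolment over about 12 months, participants answer the three-month questions in different seasons.

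Where the comparison is randomised and concurrent, both arms have the same seasonal mix, provided they share a follow-up anchor. Season then only widens the error. Aim Ia has no randomised contrast, and the split between testers and decliners is self-selected. In those analyses a predictor whose holders happened to be interviewed in another part of the year would carry a seasonal difference that reads as an association with sun protection. Aim Ia is meant to inform future messages for people given average-risk results, so a rival explanation that can be removed cheaply should be.

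**Working it through.** The documents give no seasonal figure, so there is none to reproduce. The check asks how large the effect could be under stated assumptions.

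**Inputs from the documents.** Allocation 120 and 530 (Section 8 C); up to 20% lost at three months (Section 13); 30-50% accept testing (Section 6); up to 50% of those who consider testing return a kit (Section 8 D); about 50% carry at least one high-risk variant (Section 4), so about 50% are taken to be average risk.

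**Assumptions.** Season is a yearly sine wave of amplitude A; the outcome SD without season is 1; tests are two-sided at 0.05; the power reference is 80%. The documents state none of these.

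**1. Sample sizes.**
- Randomised contrast: 120 × 0.8 = 96 and 530 × 0.8 = 424.
- Aim Ia: 530 × 0.30 × 0.5 × 0.8 = 64 to 530 × 0.50 × 0.5 × 0.8 = 106. If 50% kit return also applies, 32 to 53.

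**2. Randomised contrast.** The standard error is √(1/96 + 1/424) = 0.113, so the difference detectable with 80% power is (1.96 + 0.842) × 0.113 = 0.317 SD. With even enrolment over the year, season adds A²/2 to the variance. Power is Φ(2.80/√(1 + A²/2) − 1.96).

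| A (SD) | Added variance | Power |
|---|---|---|
| 0.1 | 0.5% | 79.8% |
| 0.2 | 2.0% | 79.2% |
| 0.3 | 4.5% | 78.2% |
| 0.5 | 12.5% | 75.2% |

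For A of 0.2 to 0.5 the loss is 0.8 to 4.8 points.

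**3. Aim Ia, group predictor (for example ethnicity).** Suppose a share f of one group is interviewed in the half-year when the curve is above its mean, and the same share of the other group in the opposite half. This is the worst alignment. The mean of the curve over a half-year is ±2A/π, so the spurious difference is (4A/π)(2f − 1). At f = 0.7 this is 1.273 × 0.3 × 0.4 = 0.15 SD for A = 0.3, and 1.273 × 0.5 × 0.4 = 0.25 SD for A = 0.5. Simulated type I error (3,000 runs per cell):

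| n | Same calendar, A = 0.3 / 0.5 | 70/30, A = 0.3 | 70/30, A = 0.5 |
|---|---|---|---|
| 32 | 0.059 / 0.055 | 0.071 | 0.096 |
| 53 | 0.052 / 0.052 | 0.087 | 0.125 |
| 106 | 0.050 / 0.052 | 0.121 | 0.239 |

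**4. Aim Ia, a belief score that is itself seasonal.** With even 12-month enrolment, n = 106 and A = 0.5 for both belief and outcome, type I error is 0.043 at a three-month lag and 0.149 at a five-month lag (2,000 runs). At A = 0.3 and a five-month lag it is 0.070. Sine and cosine terms for date bring the 0.149 back to 0.055.

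**5. Follow-up timing.** If one group is called D months later than another and enrolment lasts W months, the largest spurious difference is 2A sin(πD/12) × |sin(πW/12)/(πW/12)|. Take D = 1.5 months (assumed) and A = 0.3, so 2 × 0.3 × sin(π/8) = 0.230. For W = 6 the result is 0.230 × 0.637 = 0.15 SD; for W = 9, 0.230 × 0.300 = 0.07 SD; for an even 12 months, zero.

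**6. One set of terms or two.** Write θ for 2π × date/12. At a constant lag L, the sine and cosine of θ + 2πL/12 are linear combinations of the sine and cosine of θ. Baseline-date terms therefore add nothing to follow-up-date terms unless the lag varies.

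**The case against.** The strongest reply is that the seasonal effect is assumed and may be small. Section 4 describes the setting as one "where there is year-round sun exposure". The pilot in Section 4 reports shade-seeking "often or always while outside on a sunny day"; trial items worded in that way would remove part of the seasonal variation. The questionnaires are not in the documents, so this cannot be settled. It limits the size of the point but does not supply an adjustment.

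A reader might go further than the documents allow in three ways.

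- **That recruitment moved from clinic to clinic over the year, so the case mix must shift with season.** Nothing says so. Sections 5, 7 and 8 B list the clinics together, with no sequence. A link between a predictor and enrolment date is possible but not shown.
- **That a change between baseline and follow-up will be seasonal.** With an assumed swing of 0.3 to 0.6 points, one person could move by A√2 = 0.42 to 0.85 points over a quarter-year in the worst phase. Aim Ia does not analyse change. Even if it did, mean seasonal change is zero under even 12-month enrolment. It would reach at most 0.16 SD over 9 months and 0.33 SD over 6 months (A = 0.3, four-month lag).
- **That the randomised result is biased.** It is not, if both arms follow one anchor.

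It can also be said that Aim Ia is exploratory and its predictor list is not closed. That is fair, and it is why naming the season terms now is easy. Finally, recorded interview dates are implied by a call scheduled at three months but never stated, and the analysis is done at another institution on de-identified data. That objection stands and shapes the fix.

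**Conclusion.** The gap is real and its consequences are conditional. The items, the enrolment of about a year and the absence of any account of calendar time are all in the documents. The size is not.

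For the randomised contrast the loss is about 1 to 5 power points at amplitudes of 0.2 to 0.5 SD, with no bias if the arms share a follow-up anchor. For Aim Ia and the comparison of testers with decliners, season can confound if a predictor or group tracks enrolment date. It can also do so if follow-up timing differs while enrolment is uneven or shorter than a year, which Section 22 leaves open. The illustrative 0.15 to 0.25 SD and type I error of 0.12 to 0.24 need n = 106, amplitudes of 0.3 to 0.5 SD and a 70/30 half-year split in the worst alignment. The error is lower at n = 32 or 53, and near 0.05 when groups share a calendar.

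The documents do not support a statement that season will pass for an effect in Aim Ia. They support prespecifying a cheap adjustment that rules it out.

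**What to change.** 1. Prespecify one set of season terms, the sine and cosine of the date of the three-month interview, in every Aim I and Aim Ia sun protection model.
2. State that interview dates are recorded, and pass the month of interview to the analysts in the de-identified data. The sites should confirm that their data rules allow this.
3. Add baseline-month terms only if the lag from baseline to follow-up varies materially between participants.
4. Reconcile Sections 8 E and 11 on when the follow-up call falls due, so that testers, decliners and wait-list participants are assessed at comparable times.

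The cost is some plan wording, one extra field in the data transfer and two degrees of freedom. The last is trivial in the randomised contrast but not quite free in Aim Ia, where the analysed sample may be only about 32 to 106. Naming the terms before the data are seen is more credible than adding them afterwards.
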